Results. A group sequential trial with sample sizes of N1=180 and N2=156 at the final look achieves 91% power to detect a difference of 0.18 between a treatment group success proportion of 0.56 and a control group success proportion of 0.38 at the 0.05 significance level (alpha) using a two-sided Z-Test (Unpooled). The table below lists the sample sizes required for 91% power.

Table 5. Sample size requirements for a group sequential trial based on 100,000 iterations.

Value	95% LCL	95% UCL	Target	Actual	95% LCL	95% UCL	Beta		
0.909	0.908	0.911	0.050	0.049	0.048	0.051	0.091		
----- Average Sample Size -----									
-- Given H0 -- -- Given H1 --									
N1	N2	Grp1	Grp2	Grp1	Grp2	Diff0	Diff1	P1 H1	P2
180	156	179	155	144	125	0.00	0.18	0.56	0.38

Efficacy Monitoring. We propose to monitor efficacy at two interim time points and one final time period (i.e., three “looks”) when primary outcome data (12 month follow-up) are available for 1/3, 2/3 and 3/3 of the total sample size of VENUS subjects. For the VENUS trial, these values are provide in the following table in terms of *information time*:

Table 6. Efficacy monitoring schedule for VENUS with cumulative sample size, significance boundaries and 95%CIs, and alpha- and beta-spending.

Accumulated primary outcomes for VENUS						
Look	Accumulated Sample Size -----					
	Percent	VOM	PVAI	Total		
1	33.33	60	52	112		
2	66.67	120	104	224		
3	100.00	180	156	336		

Significance Boundaries with 95% Simulation Confidence Intervals						
Look	----- Z-Value Boundary -----			----- P-Value Boundary -----		
	Value	95% LCL	95% UCL	Value	95% LCL	95% UCL
1	+/- 3.953	3.809	4.289	0.000	0.000	0.000
2	+/- 2.543	2.516	2.578	0.011	0.010	0.012
3	+/- 2.011	1.994	2.036	0.044	0.042	0.046

Alpha-Spending						
Look	----- Target -----			----- Actual -----		
	--- Signif. Boundary---	Spending	Spending	Proportion	Cum.	
Z-Value	P-Value	Function	Function		H1 Sims	H1 Sims
Look	Scale	Scale	Alpha	Alpha	Cum. Alpha	Outside Signif. Boundary
1	+/- 3.953	0.000	0.000	0.000	0.000	0.033
2	+/- 2.543	0.011	0.012	0.011	0.012	0.547
3	+/- 2.011	0.044	0.038	0.038	0.049	0.329
						0.909
		Spent	Spent	Boundary		Cum. Boundary

The hypothesis test applied at the k th look is a two-tailed test of equality of two independent proportions, functionally composed as

$$Z_k = \frac{\hat{p}_{1k} - \hat{p}_{2k}}{\sqrt{\frac{\hat{p}_{1k}(1-\hat{p}_{1k})}{n_{1k}} + \frac{\hat{p}_{2k}(1-\hat{p}_{2k})}{n_{2k}}}}$$

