where \hat{p}_{1k} is the proportion of successful primary outcomes in the PVAI-VOM arm of VENUS at the k th look, and \hat{p}_{2k} is the proportion of successful primary outcomes within the PVAI arm of VENUS at the k th look. Z_k follows a standard normal distribution, $N(0,1)$. If during the first look when at least $N=60$ VOM and $N=52$ PVAI primary outcomes have been observed ($N=112$ total), if Z_1 exceeds 3.953, then the trial will be evaluated for early termination due to beneficial efficacy, whereas if the power is 30% or less, the trial will be evaluated for early termination for futility. However, if the power of the test falls in the “promising zone” (30-70%), we will continue the trial. The same rule applies for the 2nd look when at least $N=120$ VOM and 104 PVAI primary outcomes (224 total) have been observed in both arms, for which the tabled critical value of Z_2 is ± 2.543 . The overall efficacy of the trial will be determined when at least $N=180$ VOM and $N=156$ (336 total) primary outcomes have been observed, for which the critical value of Z_3 is ± 2.011 .

[figure not shown]

Figure S1. Efficacy boundaries at 33%, 66%, and 100% accrual of VENUS primary outcomes.

VENUS Interim Analysis - Conditional Power and Futility For Various Test Results.

During the interim analysis, estimations of conditional power and futility will be performed, to provide information for clinical trial continuation decisions. The sample size will not be subject to any changes.

Conditional power runs were made using PASS 12 (Kaysville, UT). During the first look at 33% information time, there will be 60 VOM and 52 PVAI primary outcomes available. Using a one-sided ($\alpha=0.025$) test of two proportions, $\theta=p_2-p_1$, where p_2 is the PVAI success rate and p_1 is the VOM success rate, the expectation is that the test statistic Z_k is less than zero, since $H_a: p_2 < p_1$. The table below list the conditional power and futility at the first look for a range of Z_k values:

Table 7. VENUS Conditional power and futility at the first look (33% information, 60 VOM, 52 PVAI) for a range of Z_k values from a one-sided test of two independent proportions.

Cond. Power	Pred. Power	Total Sample Size VOM/PVAI	Current Sample Size n1k n2k	Prop. Group 1 P1	Prop. Group 2 P2	Test Statistic Z _k	Alpha	Futility
0.99994	1	180 156	60 52	0.56	0.38	-5	0.025	0.00006
0.99974	0.99998	180 156	60 52	0.56	0.38	-4.5	0.025	0.00026

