	95% LCL	95% UCL	Target	Actual	95% LCL	95% UCL			
0.810	0.807	0.812	0.050	0.049	0.047	0.050	0.190		
----- Average Sample Size -----									
-- Given H_0 -- -- Given H_1 --									
N1	N2	Grp1	Grp2	Grp1	Grp2	Diff0	Diff1	P1 H1	P2
33	33	33	33	28	28	0.00	0.34	0.76	0.42

Results. Group sequential trials with sample sizes of 33 and 33 at the final look achieve 81% power to detect a difference of 0.34 between a treatment group proportion of 0.76 and a control group proportion of 0.42 at the 0.05 significance level (alpha) using a two-sided Z-Test (Unpooled).

Efficacy Monitoring. We propose to monitor efficacy at two interim time points and one final time period (i.e., three “looks”) when primary outcome data (12-15 month follow-up) are available for 1/3, 2/3 and 3/3 of the total sample size of MARS subjects. For the MARS trial, these values are provide in the following table in terms of *information time*:

Table 10. Efficacy monitoring schedule for MARS with cumulative sample size, significance boundaries and 95%CIs, and alpha- and beta-spending.

Accumulated primary outcomes for MARS												
Look	Information Percent	Accumulated Sample Size			Z-Value Boundary			P-Value Boundary				
		Group 1	Group 2	Total	Value	95% LCL	95% UCL	Value	95% LCL	95% UCL		
1	33.33	11	11	22								
2	66.67	22	22	44								
3	100.00	33	33	66								
Significance Boundaries with 95% Simulation Confidence Intervals for Scenario 1												
----- Z-Value Boundary -----			----- P-Value Boundary -----									
Look	Value	95% LCL	95% UCL	Value	95% LCL	95% UCL	Value	95% LCL	95% UCL	Value	95% LCL	95% UCL
1	+/- 5.014	5.014	6.675	0.000	0.000	0.000						
2	+/- 2.708	2.640	2.708	0.007	0.007	0.008						
3	+/- 2.055	2.055	2.080	0.040	0.037	0.040						
Alpha-Spending												

Look	----- Target -----		----- Actual -----		Proportion		Cum.		H1 Sims		H1 Sims	
	-- Signif.	Boundary--	Spending	Spending	Cum.	Alpha	Cum.	Alpha	Outside	Signif.	Outside	Signif.
Z-Value	Scale	P-Value	Scale	Function	Alpha	Spent	Alpha	Spent	Boundary	Signif.	Boundary	Signif.
1	+/- 5.014	0.000	0.000	0.000	0.000	0.000	0.000	0.000	0.017	0.017	0.422	0.422
2	+/- 2.708	0.007	0.012	0.012	0.010	0.010	0.011	0.011	0.404	0.404	0.810	0.810
3	+/- 2.055	0.040	0.038	0.050	0.038	0.038	0.049	0.049	0.388	0.388		

[figure not shown]

Figure S2. Efficacy boundaries at 33%, 66%, and 100% accrual of MARS primary outcomes.

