During the interim analysis, estimations of conditional power and futility will be performed, to provide information for clinical trial continuation decisions. The sample size will not be subject to any changes.

Table 11. MARS Conditional power and futility at the first look (33% information, 11 VOM, 11 PVAI) for a range of Z_k values from a one-sided test of two independent proportions.

Cond. Power	Pred. Power	Total Sample Size VOM/PVAI	Current Sample Size n1k n2k	Prop. Group 1 P1	Prop. Group 2 P2	Test Statistic Z_k	Alpha	Futility
0.9997	1	33 33	11 11	0.76	0.42	-5	0.025	0.0003
0.99894	0.99998	33 33	11 11	0.76	0.42	-4.5	0.025	0.00106
0.99674	0.99978	33 33	11 11	0.76	0.42	-4	0.025	0.00326
0.99104	0.99814	33 33	11 11	0.76	0.42	-3.5	0.025	0.00896
0.97798	0.98894	33 33	11 11	0.76	0.42	-3	0.025	0.02202
0.95155	0.95313	33 33	11 11	0.76	0.42	-2.5	0.025	0.04845
0.90431	0.85624	33 33	11 11	0.76	0.42	-2	0.025	0.09569
0.82969	0.67408	33 33	11 11	0.76	0.42	-1.5	0.025	0.17031
0.72555	0.43598	33 33	11 11	0.76	0.42	-1	0.025	0.27445
0.5971	0.2196	33 33	11 11	0.76	0.42	-0.5	0.025	0.4029
0.45712	0.08289	33 33	11 11	0.76	0.42	0	0.025	0.54288

Table 12. MARS Conditional power and futility at the second look (66% information, 22 VOM, 22 PVAI) for a range of Z_k values from a one-sided test of two independent proportions.

Cond. Power	Pred. Power	Total Sample Size VOM/PVAI	Current Sample Size n1k n2k	Prop. Group 1 P1	Prop. Group 2 P2	Test Statistic Z_k	Alpha	Futility
1.00000	1.00000	33 33	22 22	0.76	0.42	-5	0.025	0
1.00000	1.00000	33 33	22 22	0.76	0.42	-4.5	0.025	0
0.99995	0.99998	33 33	22 22	0.76	0.42	-4	0.025	0.00005
0.99925	0.9995	33 33	22 22	0.76	0.42	-3.5	0.025	0.00075
0.99323	0.99233	33 33	22 22	0.76	0.42	-3	0.025	0.00677
0.96097	0.94042	33 33	22 22	0.76	0.42	-2.5	0.025	0.03903
0.85426	0.75562	33 33	22 22	0.76	0.42	-2	0.025	0.14574
0.636	0.43104	33 33	22 22	0.76	0.42	-1.5	0.025	0.364
0.35968	0.14923	33 33	22 22	0.76	0.42	-1	0.025	0.64032
0.14311	0.02834	33 33	22 22	0.76	0.42	-0.5	0.025	0.85689
0.03807	0.00279	33 33	22 22	0.76	0.42	0	0.025	0.96193

C) Statistical Analyses.

Pre-specified subgroup analyses: The following subgroups are defined to assess potential impact on outcomes:

- Male vs female.

- Longstanding persistent AF (duration of more than 1 year) vs persistent AF of less than one year
- Left atrial volume strata: defined as mild or no left atrial enlargement (LA volume - up to 75 ml/m²), moderate enlargement (76-89 ml/m²), or severe enlargement -90+ ml/m²)

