- Enrollment as AF or AT –for MARS-AF trial only.
- Pre-existing low voltage scar and extent of low-voltage scar after ablation procedure (divided in tertiles).

Primary Outcome. Hypothesis tests for the equality of two proportions (unpooled standard errors) will be employed for determining whether or not the VOM success rate is significantly greater than the success rate for PVAI. The test statistic is a z-score which is standard normal distributed and the relevant lookup critical values (percentage points) are listed in the interim analysis section for group sequential designs. From a post-hoc perspective, we may use the stratified Mantel-Haenszel odds ratio test of proportions if we learn that success rates track with a particular covariate, such as LA volume or AF duration, and the strata weights are not highly imbalanced.

Secondary Outcomes. The secondary outcomes are listed below along with their corresponding storage location (various tables or Excel .csv files on output after report generation). Model building strategies (MBS) will be employed using univariate and multivariable regression models for post-hoc analyses of secondary outcomes. During MBS, univariate predictors whose $p < 0.25$ will be selected as multiple variable model candidates. MBS regression methods may include linear, logistic, Poisson, and Cox proportional hazards (PH) along with regression diagnostics using the relevant goodness-of-fit criteria, residuals, variance inflation factors (VIF), ROC-AUC, and assumption-checking techniques (e.g. normally-distributed standardized residuals for linear regression). Regression diagnostics for linear regression will include estimation and filtering of overly influential records based on residuals, standardized residuals, deletion residuals, Cook's distance, leverage, DFFITS, DFBETAS, and VIFs. Regression diagnostics for logistic and Poisson regression will include filtering on Pearson, deviance, and leverage residuals and the Hosmer-Lemeshow test for logistic regression GOF. Cox PH regression diagnostics will include Schoenfeld and Nelson-Aelen residuals, and possible employment of stratified models when the PH assumption fails.

The table below lists the primary outcomes which are to be analyzed during each interim analysis, as well as the secondary outcomes which will be analyzed and reported prior to all DSMB review meetings.

Primary Endpoints	EDC Pages	Data Fields

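### Conditional and predictive power in Tables 7, 8, 11 and 12 are computed for a 1.96 test, and conditional power with a pooled-type variance, not for the unpooled final tests at 2.011 (VENUS) and 2.055 (MARS); the net conditional-power error is at most about 2.2 points

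*Combined protocol and SAP*

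**What the plan says.** All references are to section 6.0 of the combined protocol and SAP.

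- **Final test.** Table 6 sets the third-look boundary at ±2.011 for VENUS, and Table 10 sets it at ±2.055 for MARS. Both design lists name an unpooled Z-test, and the formula for Z at each look in part B uses unpooled variances. The Primary Outcome paragraph repeats unpooled standard errors and says the "critical values (percentage points) are listed in the interim analysis section for group sequential designs".
- **Conditional power.** Part B states that "Conditional power runs were made using PASS 12 (Kaysville, UT"), with a one-sided alpha of 0.025. The captions of Tables 7, 8, 11 and 12 describe Z values "from a one-sided test of two independent proportions", and every row carries alpha 0.025. A typical row, from Table 12, captioned "MARS Conditional power and futility at the second look (66% information, 22 VOM, 22 PVAI"), reads "0.35968 0.14923 33 33 22 22 0.76 0.42 -1 0.025 0.64032": conditional power, predictive power, final and current sizes, the two rates, Z, alpha, and one minus conditional power.
- **Use.** The VENUS text says "whereas if the power is 30% or less, the trial will be evaluated for early termination for futility" and calls 30-70% the zone in which the trial continues. The MARS text gives no threshold. Both say the estimates will inform continuation decisions.
- **Assumed rates.** VENUS assumes a "treatment group success proportion of 0.56 and a control group success proportion of 0.38". MARS assumes a "treatment group proportion of 0.76 and a control group proportion of 0.42".

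**The concern.** Conditional power is the chance, given the interim result, of passing the test that will be applied at the end. A one-sided 0.025 test has a critical value of 1.96, and neither trial ends with that value. The tables therefore seem to describe an easier final test than the planned one and to make a weak interim result look more promising than it is.

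Both designs state that there is no futility boundary. These power figures are then the only quantitative futility guide the monitoring board gets, and in VENUS they are read against a 30% line. A bias in them shifts the interim Z at which the board is asked to consider stopping.

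**Working it through.** **Formula.** Write z for the interim Z in favour of VOM (the tables print it as -z). Let I_k and I_K be the information at the look and at the end, D = I_K - I_k, d = p1 - p2, and c the final cut-off.

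CP = Phi[(z·√I_k - c·√I_K + d·D) / √D]

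- Pooled-type information: I = 1/[m(1-m)(1/n1+1/n2)], with m = (p1+p2)/2.
- Unpooled information: I = 1/[p1(1-p1)/n1 + p2(1-p2)/n2].

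**Step 1: reproduce the plan (c = 1.960, pooled-type).**

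- Table 12, Z=-1: m = 0.59 and m(1-m) = 0.2419, so I_k = 45.47, I_K = 68.21, D = 22.74. Numerator = 6.743 - 16.187 + 7.730 = -1.713. Divided by 4.768 this is -0.359, and CP = 0.3597. Printed: 0.35968.
- Table 8, Z=-1: m = 0.47 and m(1-m) = 0.2491, so I_k = 223.66, I_K = 335.49, D = 111.83. Numerator = 14.955 - 35.900 + 20.130 = -0.815. Divided by 10.575 this is -0.077, and CP = 0.4693. Printed: 0.46930.

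All 44 printed conditional-power values reproduce to five decimals in this way. With the same variance and c = 2.011 or 2.055, the largest misfits are 0.024, 0.035, 0.046 and 0.063 (Tables 7, 8, 11, 12). The unpooled variance fits with neither cut-off.

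**Step 2: put in the plan's own final test (unpooled, final boundary).**

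- Table 12, Z=-1, c = 2.055: p1(1-p1) + p2(1-p2) = 0.1824 + 0.2436 = 0.4260, so I_k = 22/0.426 = 51.64, I_K = 33/0.426 = 77.46, D = 25.82. Numerator = 7.186 - 18.087 + 8.779 = -2.121. Divided by 5.081 this is -0.417, and CP = 0.338.
- Table 8, Z=-1, c = 2.011: I_k = 231.55, I_K = 347.33, D = 115.78. Numerator = 15.217 - 37.478 + 20.840 = -1.422. Divided by 10.760 this is -0.132, and CP = 0.447.

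| Table | Z | Printed | Cut-off changed only | Cut-off and variance changed |
|---|---|---|---|---|
| 7 (VENUS look 1) | 0 | 0.615 | 0.591 | 0.609 |
| 8 (VENUS look 2) | -1.5 | 0.736 | 0.706 | 0.717 |
| 8 | -1 | 0.469 | 0.434 | 0.447 |
| 8 | -0.5 | 0.216 | 0.191 | 0.201 |
| 11 (MARS look 1) | -1 | 0.726 | 0.685 | 0.737 |
| 11 | 0 | 0.457 | 0.411 | 0.471 |
| 12 (MARS look 2) | -1.5 | 0.636 | 0.573 | 0.614 |
| 12 | -1 | 0.360 | 0.300 | 0.338 |
| 12 | -0.5 | 0.143 | 0.109 | 0.130 |

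**Step 3: the Z that gives 30% at look 2.** Solve with Phi^-1(0.30) = -0.524: z = (-0.524·√D + c·√I_K - d·D)/√I_k.

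- VENUS as printed: (-5.546 + 35.900 - 20.130)/14.955 = 0.68. Corrected: (-5.643 + 37.478 - 20.840)/15.217 = 0.72.
- MARS as printed: (-2.501 + 16.187 - 7.730)/6.743 = 0.88. Corrected: (-2.665 + 18.087 - 8.779)/7.186 = 0.92.

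At look 1 every tabulated conditional power is above 30%. The lowest printed values, at Z=0, are 0.615 and 0.457.

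**Step 4: predictive power.** The printed values reproduce as Phi[(z·√I_K - c·√I_k)/√D] with c = 1.960. Only the information fraction enters, so the variance choice cancels and does not offset the cut-off. At look 2 the expression is Phi(z·√3 - c·√2). At Z=-1.5, printed 0.431 in both trials, it gives Phi(2.598 - 2.844) = 0.403 for VENUS (2.8 points lower) and Phi(2.598 - 2.906) = 0.379 for MARS (5.2 points lower).

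**The case against.** The strongest counter-argument is that the cut-off is only one of two mismatched inputs. A reader who changes the cut-off alone might infer that conditional power is overstated by up to 6.3 points in MARS and 3.5 in VENUS, that MARS look 2 at Z=-1 lands on the 30% line (0.300), and that MARS look 1 at Z=-1 drops below 70% (0.685). The documents do not support this. The trial's test is unpooled throughout, and for that test the figures are 0.338 and 0.737. Table 11 is in fact slightly too low. Changing only the cut-off would move several MARS rows further from the trial's own test than they are now. This part of the objection stands in full for conditional power.

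It also stands that the 30% line and the 30-70% zone are written only in the VENUS text, so applying them to MARS is an inference, although the stopping rules cover both trials. Crossing 70% downward would trigger nothing, because the plan says to continue in that zone. Low power leads only to an evaluation for stopping, and the tables state their alpha openly.

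A further objection is that the printed rows are illustrations and the board's figures will be computed at the interim. That does not remove the problem. The only stated method for those figures is the one used in the tables, so without a correction the mismatch carries over to the real calculation.

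**Conclusion.** The mismatch is real, and its effect on conditional power is small. With the boundary and the variance both taken from the plan, Tables 8 and 12 are up to about 2.2 points too high, Table 7 is under 1 point too high, and Table 11 is up to 1.4 points too low. The near-agreement arises only because two inconsistencies partly cancel. They do not cancel for predictive power, which falls by up to 5.2 points in Table 12. This matters because the 30% rule does not say which kind of power it means, and at MARS look 2, Z=-1, the printed values are 0.360 and 0.149.

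No tabulated row of either quantity crosses 30%; the effect is on interim results between the rows. A reader might also infer a loss of type I error control. There is none, since the efficacy boundaries are untouched and futility is non-binding.

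The figures assume the plan's rates and the section 6.0 sample sizes (33+33 for MARS). The look-1 values ignore stopping for efficacy at look 2, which changed the rows checked (Z=0 to -1) by only about 0.2 points.

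**What to change.** Re-run Tables 7, 8, 11 and 12 with final critical values 2.011 (VENUS) and 2.055 (MARS) and the unpooled variance. State that interim conditional and predictive power will be computed the same way, and use those values for the 30% futility evaluation. Change both inputs together.

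Before the run, reconcile the MARS sizes: the synopsis gives 37+32 = 69, and section 6.0 gives 33+33 = 66. If the reconciled size changes the simulated MARS boundary, use the new one. In the same edit, say whether the 30% rule refers to conditional or predictive power and whether it applies to MARS.

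The cost is one software run, four replaced tables and a sentence or two of text. Sample size, efficacy boundaries and conduct do not change, apart from any MARS boundary update that the size reconciliation requires.

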3.0 INNOVATION

The basis of this application is an entirely novel technique that was developed in our laboratory from its original conception, to its validation in animals,¹⁵ to the demonstration of safety and feasibility in humans.¹⁶ Ethanol is used in hypertrophic cardiomyopathy,⁶⁴ and in ventricular tachycardias that do not respond to conventional RF ablation.⁶⁵ When delivered in the VOM, we have shown that ethanol can help ablate neighboring atrial tissues, all of which are routinely targeted during conventional ablation.¹⁵ Supported by an R21 grant that started in July 2010, significant human pilot data have been acquired that lend further support to the mechanistic rationale, safety, and potential clinical utility of this technique.

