3.2 VOM ETHANOL INFUSION: TECHNIQUE

We have refined the technique over the past 3 years. We enter the CS with a sheath advanced from the right internal jugular vein. A sub-selector catheter with a ~90° angle at the tip (typically, a left internal mammary artery angioplasty guide catheter) is advanced through the CS sheath with its tip pointing superiorly and posteriorly. Contrast injections through the sub-selector catheter help identify the VOM and direct the catheter tip to the VOM ostium. Then, an angioplasty wire is inserted into the VOM, over which an angioplasty balloon is advanced distally into the VOM. Contrast injections through the angioplasty balloon help delineate the size and branching patterns of the VOM. Ethanol injections are then delivered (up to four injections of 1 cc over 2 minutes each), each at different levels of the VOM –from distal in the VOM, where the first injection is delivered, the balloon is retracted ~1 cm after each injection until the balloon reaches the VOM ostium or 4 injections are given. [Figure 3](#) shows an example.

Figure 3. VOM cannulation technique and LA venous plexus.

A, Contrast injection in the CS lumen through the sub-selector catheter with its tip close to the VOM, showing the VOM take-off and branching patterns outlined in **B**. **C**, selective venogram via an angioplasty balloon in a VOM branch. Collaterals fill LA veins in the LA roof (outlined in **D**).

In our experience to date, we have been able to perform successful cannulation of the VOM and to complete the protocol of ethanol infusion in 89 of a total of 106 patients (85%). Our success rates in the last half of the patients versus the first half have been higher (90% vs. 73%, $p<0.05$), suggesting that success is not only determined by anatomical factors (e.g., size and tortuosity of the VOM), but also by operator experience.

[figure not shown]

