2. In patients randomized to VOM ethanol infusion:
 - a. Successful vs. unsuccessful cannulation with angioplasty wire and balloon.
 - b. Extent of tissue ablation achieved by ethanol infusion, defined as areas with local electrogram voltage <0.1 mV on 3D mapping. (Pre-PVAI voltage map).
 - c. Added procedural and fluoroscopy time.
 - d. Effect on AF: termination, conversion into flutter or no change.
 - e. RF time to achieve block around the mitral annulus.
 - f. Complications related to VOM instrumentation.
 - g. Blood ethanol level measurement.
 - h. LA instrumentation time.
 - i. Ablation lesion sets: 3D maps (Carto or NavX) including total (RF plus ethanol) ablated scar surface area, as measured by bipolar voltage less than 0.1 mV
 - j. Periprocedural data collection.

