5.5 STUDY PROCEDURES

SCREENING/BASELINE

1. Initial assessment.

After signing informed consent, the following data will be collected; a significant medical history and recent targeted physical exam, electrocardiogram (EKG), echocardiogram within one year prior to the procedure for evaluation of cardiac structure, and function, and laboratory tests. In addition, a review of medications that patient is taking (limited to AAD and anticoagulants), and a quality of life (QOL) questionnaire especially developed for AF (AFEQT)¹¹³ will be filled out by patients.

Screening assessments performed pre-consent signature that are completed under standard of care can be included as viable source documents for patient study inclusion/exclusion and may be collected to screen potential study patients.

2. Pre-procedural imaging.

Imaging prior to enrollment is required to rule out structural heart disease and, as needed, to rule out the presence of LA appendage thrombus. *Ruling out LAA thrombus can be performed by the following: TEE, CT or MRI within 48 hours of the*

procedure; at least one month of oral anticoagulation prior to the procedure; or documented prior procedures of LAA occlusion or ligation. For ruling out structural heart disease, either a cardiac MRI, CT or transthoracic echocardiogram within 1 year prior to participation in the study is sufficient. Documentation by exception (ie. no LAA thrombus documented on imaging report) is permitted for determination of eligibility. Left atrial diameter and estimated left atrial volume will be obtained from any of these diagnostic modalities. There is no specific requirement for a pre-ablation CT or MR, since anatomical details of the LA can be obtained intra-procedurally with current mapping systems.

3 Randomization.

Randomization should take place after confirmation that all inclusion/exclusion criteria are met and measurements of LA volume are obtained. Patients will be randomized in a 1.15:1 fashion (to account for an 85% technical feasibility of the VOM procedure) to receive either VOM-PV or the conventional PVAI. Patients will be blinded to the randomization outcome.

PROCEDURE/DAY 0:

1 PVAI procedure

As part of a conventional catheter ablation of AF the following will be performed, all considered standard of care:

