- a) Electrophysiological catheters will be inserted, including a CS catheter, a duodecapolar circumferential catheter, and an ablation catheter. The last two will be inserted in the LA via trans-septal punctures.
- b) Prior to ablation, geometry of the LA will be obtained using a 3-dimensional (3D) mapping system (any of the commercially available systems). This will generate a computerized geometry of the LA, including baseline voltage amplitudes in different regions. LA scar surface area (bipolar voltage less than 0.1 mV) will be collected.
- c) Lesion sets delivered by RF application will include, in a step-wise fashion, the following ablations, starting with PVAI and added sequentially per the operator's judgment if AF persists after each step is completed:
 - i) PVAI. RF should be applied 1 cm proximal to the PV ostia in a wide area circumferential pattern. Isolation will be verified by the absence of electrical activity from each PV and/or dissociated activity.
 - ii) The greater PV antra, including posterior wall and roof.
 - iii) Mitral isthmus: a line of RF ablation from the left inferior PV to the mitral annulus. Bidirectional block should be verified after completion by differential pacing.

- iv) Areas of complex, fractionated potentials.
- v) Sustained atrial flutters will be mapped and ablated as directed by the map and flutter location.
- vi) Following step 4c, if AF persists after all the RF ablations, the patient will be cardioverted to restore sinus rhythm. Given the potential variability of the extent of ablations, maps of the lesion sets (see below) will be collected and maintained in an imaging core laboratory.

2 VOM procedure

In patients randomized to VOM-PV, ***prior to the conventional PVAI***, the following will be performed:

- a) A 7F-9F sheath will be advanced in the CS via a right internal jugular vein access. Femoral vein access is also appropriate to cannulate the CS. Contrast injection in the CS will be performed via a sub-selector catheter (recommended 6F left internal mammary angiographic guide catheter) to identify the VOM. We will obtain a CS venogram and identify the location of the VOM. Cannulation of the VOM will be performed using the sub-selector catheter that can be torqued so that its tip is engaged in the ostium of the VOM. Contrast will be injected via the lumen of the sub-selector catheter to verify such engagement.

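### The pre-specified subgroups include scar measured after the randomised procedure; comparing arms within its tertiles would not be a randomised comparison

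*Combined protocol and SAP*

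**What the plan says.** The pre-specified subgroup list is in section 6.0 (Statistical Analyses). Its only stated purpose is this: "The following subgroups are defined to assess potential impact on outcomes". The list covers sex, AF duration, left atrial volume and, for MARS, enrolment rhythm. A final bullet joins two scar measures: low-voltage scar present beforehand, and "extent of low-voltage scar after ablation procedure (divided in tertiles").

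Other sections show what the second measure is:

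- **Timing.** Section 5.5 randomises patients before the procedure. It schedules the last voltage map once the ablation lesions are finished, in both arms.
- **Content.** The procedural data list at the end of section 4.2 has the VOM-PV arm recording maps "including total (RF plus ethanol) ablated scar surface area".
- **Operator influence.** Under section 5.5, RF steps are added on the operator's "judgment if AF persists after each step is completed". Section 7.6 tells operators the assignment.
- **Role as an outcome.** Section 5.2 includes the extent of ablated left atrial tissue in secondary endpoint 4. The section 6.0 endpoint table gives scar measurements as its data.

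No section states whether arms are compared within scar tertiles or scar is only related to outcome, whether tertiles are cut pooled or by arm, or that this subgroup is not protected by randomisation.

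**The concern.** A subgroup analysis is a randomised comparison only if the assigned treatment cannot change the grouping variable. Post-procedure scar fails that test in three ways:

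- Ethanol adds to it directly.
- Ethanol may also lower it, because section 7.8 expects less RF in the areas ethanol reaches.
- Lesions are added while AF persists, by an operator who knows the arm, so the total also reflects how hard the AF was to treat.

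A given tertile can therefore contain patients with different underlying prognosis in the two arms. A by-arm comparison inside it could create a difference or hide one. Because ethanol is meant to work partly by ablating tissue, holding final scar fixed may also remove part of the effect under study.

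The practical risk is a table that carries the authority of pre-specification and is read as showing that VOM infusion works only, or fails, when scar is extensive. It could not support that reading.

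**Working it through.** **1. Design figure.** The plan gives 91% power for VENUS (180 v 156; 0.56 v 0.38; unpooled Z).

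- SE = √(0.56×0.44/180 + 0.38×0.62/156) = 0.0537, so the expected Z is 0.18/0.0537 = 3.35.
- At the final boundary of 2.011, power is Φ(3.35 − 2.011) ≈ 0.91.

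The plan's figure reproduces, and nothing below touches it.

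**2. Inputs for tertile make-up (VENUS).**

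| Input | Value | Source |
|---|---|---|
| VOM-PV share overall | 180/336 = 54% | Section 6.0 |
| Ethanol lesion | 9.7 ± 4.8 cm² | Section 3.4 |
| Proportion with a lesion, r | 85%; also 73% and 90% | See below |
| SD of RF scar | 5, 10, 20 cm² | Assumed |
| Share of lesion that is net new scar, f | −0.5, 0, 0.5, 1 | Assumed |

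The 85% is the plan's allowance "to account for an 85% technical feasibility of the VOM procedure" in section 5.5. Section 3.2 reports cannulation and completed infusion "in 89 of a total of 106 patients (85"%); 89/106 is 84.0%, a trivial difference. It also reports "Our success rates in the last half of the patients versus the first half have been higher (90% vs. 73"%), hence the two alternatives. Using any of these as the lesion rate is an assumption.

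**3. Model.** Scar = Normal(RF scar) + f × Normal(9.7, 4.8) in a fraction r of the VOM-PV arm. Tertiles are cut pooled, with 1.5 million simulated patients per setting.

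VOM-PV share in the lowest / highest tertile at r = 85%:

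| f | SD 5 | SD 10 | SD 20 |
|---|---|---|---|
| −0.5 | 75% / 35% | 65% / 43% | 59% / 48% |
| 0 | 54% / 54% | 54% / 54% | 54% / 54% |
| 0.5 | 35% / 75% | 43% / 65% | 48% / 59% |
| 1 | 25% / 90% | 35% / 75% | 43% / 65% |

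For f from 0.5 to 1, the range is 31–49% / 58–85% at r = 73% and 23–48% / 60–91% at r = 90%. The fully additive row is the least supported. Section 3.0 says of the tissues ethanol reaches that they are "all of which are routinely targeted during conventional ablation", so RF would often have ablated them anyway. The negative row represents ethanol replacing more RF scar than it makes.

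**4. Precision.** A tertile holds 336/3 = 112 patients. The 95% CI half-width is 1.96 × √(0.56×0.44/n₁ + 0.38×0.62/n₂):

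- 60 v 52 (54% share): 18.2 points
- 84 v 28 (75% share): 20.9 points
- 101 v 11 (90% share): 30.3 points

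**5. Can imbalance become bias?** This step is illustrative only, because the documents give no distribution of final scar by arm. Suppose treatment has no effect, and an unmeasured severity factor correlates 0 to 0.7 with scar and lowers the log-odds of success by 0.7 to 1.0 per SD. The mean within-tertile difference between arms, by how far treatment shifts scar, is:

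| Shift (within-arm SDs) | Difference when the correlation is 0.3–0.7 |
|---|---|
| 0 | 0 |
| +0.5 | +0.02 to +0.06 |
| +1 | +0.04 to +0.11 |
| +2 | +0.07 to +0.21 |
| −1 | −0.04 to −0.11 |

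The difference is zero at every shift if the correlation is zero. The whole-trial difference stays at zero throughout. Conversely, if the planned 0.18 benefit acted wholly through scar (shift of 1 to 2 SD), the within-tertile differences would shrink to about 0.01 to 0.05.

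**The case against.** The strongest reply is that section 6.0 speaks only of impact on outcomes. It does not mention treatment effect or interaction, so the authors may have meant a prognostic question: does more scar go with more success? On that reading no randomised comparison is broken. This stands as a possibility, and the point is conditional on it. But the text does not choose, and the item sits in a list of ordinary baseline subgroups, which invites a by-arm table.

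Other objections have partial force:

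- The bullet itself says the scar is measured after ablation. It discloses timing, but not what can be inferred.
- None of the subgroups has a stated analysis. That is true, but the others are not effects of the procedure, so a by-arm comparison within them keeps the protection of randomisation.
- The imbalance depends on assumed inputs, can run either way, and vanishes with zero net scar shift. All of this is correct. With by-arm tertiles the share is 54% by construction, but the same tertile then means different scar ranges whenever treatment moves scar.
- Baseline scar may be a weak substitute in VENUS, because footnote (b) to the schedule in section 7.1 expects little or none before a first procedure. This is a fair limit on what the retained subgroup can show. It does not make the post-procedure one valid.
- In MARS, final scar can include scar from the earlier ablation, so it is not identical to tissue ablated in this trial. This bears on how scar is reported by arm, not on the main point.

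**Conclusion.** The concern holds. The plan pre-specifies a subgroup on a variable that is measured after randomisation, includes part of the assigned treatment, and is also treated as an outcome. A comparison of arms within its tertiles would not be a randomised comparison, and nothing elsewhere in the plan relabels or repairs it.

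The size of any bias cannot be derived from the documents. The tertile shares and within-tertile differences above rest on an assumed RF-scar SD, net scar share and link between scar and prognosis; they show what could happen and are not estimates. The conclusion depends only on treatment being able to change the scar measure, which the plan itself states.

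The consequence is confined to this subgroup table. The primary test, sample size, stopping boundaries and secondary endpoints are unaffected. It should be corrected, but it does not threaten the main result.

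**What to change.** Split the scar bullet in section 6.0.

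- **Remove** post-procedure scar extent from the pre-specified subgroups.
- **Keep** pre-existing scar, with its cut fixed before outcome data are seen. Confirm that the map used precedes both ethanol and RF. The map list in section 5.5 implies this, although the same section also describes baseline mapping within the PVAI step that follows ethanol. If VENUS baseline scar has too little spread for tertiles, choose a simpler cut, also before outcomes are seen.
- **Report** post-procedure scar by arm under secondary endpoint 4, saying how scar from an earlier ablation is handled in MARS.
- **Label** any analysis relating post-procedure scar to outcome as exploratory, post-randomisation and non-randomised. State whether it is prognostic or a mediation analysis, and whether tertiles are pooled or by arm.

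The cost is half a bullet and one label in the SAP. The plan already collects the baseline map in both arms, so no new data are needed. One pre-specified subgroup table is lost, and the scientific question about scar is kept under an accurate description.
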